- 2- The lack of knowledge and information in the published studies about the effect of resisted exercise on improving insulin resistance post-burn.
- 3- This study will be carried out to investigate the effectiveness of resisted exercise in improving insulin resistance in post-burned patients.

The hyper metabolic response to injury is characterized by increased blood pressure and heart rate, peripheral insulin resistance, and increased protein and lipid catabolism, which lead to increased resting energy expenditure, increased body temperature, total body protein loss, muscle wasting, and stimulated synthesis of acute-phase proteins. These responses occur in all trauma, surgical, or critically ill patients, but the magnitude with which they occur and their duration are particularly severe and sustained for burn patients (**Gerd G Gauglitz et al, 2022**).

Delimitation

This study will be delimited in the following aspects:

Subjects

Sixty eight patients with insulin resistance post burn will participate in this study, they will be selected from government hospitals (general and insurance).

Will be randomly divided into two equal groups (group A, group B).

Their ages range from 18-35 years.

Equipment and tools:

Measurement:

Insulin resistance homeostasis model assessment [HOMA IR test].

Null hypothesis

There will be no effect for resisted exercise on insulin resistance post burn.

Basic assumption

It will be assumed that:

- All patients will be evaluated in the same way.
- All patients will be cooperative and follow instructions during the assessment procedures.
- The results obtained from this study will be of value in the physical therapy field.

Definition of terms:

The following terms will be defined and explained for a clear understanding of the terminology used in this study:

Insulin resistance

Insulin resistance is defined as the decreased tissue response to insulin-mediated cellular actions and is the inverse of insulin sensitivity. The term “insulin resistance,” as generally applied, refers to whole-body reduced glucose uptake in response to physiological insulin levels and its consequent effects on glucose and insulin metabolism. Euglycemic hyperinsulinemic clamp studies have shown that insulin resistance is determined primarily by the response of skeletal muscle, with over 75% of infused glucose taken up by muscle and only 2–3% by adipose tissue (**Claire**

Levy-Marchal et al, 2010).

Chapter II

Literature review

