described in percentage terms from 100% as the median norm. However, scales of percentages raise their own problems, since statements describing a percentage change can be ambiguous—a change on the scale from 50% to 60% is a 10% change in units but a 20% relative change (**T. M. Wallace, D. R. Matthews, 2002**).

The changes in patient metabolism following a major burn may be seen for more than 12 months after the initial injury. The ensuing period of hypermetabolism and catabolism post-burn leads to impaired immune function, decreased wound healing, erosion of lean body mass, and hinders rehabilitative efforts delaying reintegration into normal society. The typical changes in metabolism are the development of a hyperdynamic circulation, increased body temperature, increased protein catabolism with peripheral protein wasting, increased lipolysis leading to fatty infiltration of the liver, increased glycolysis and insulin resistance. These changes are responsible for much of the morbidity and mortality seen with such an injury and as such are important targets for available treatments including: early excision and grafting; aggressive treatment of burn, early commencement of high protein, high carbohydrate enteral feeding, elevation of the immediate environmental temperature to 31.5°C ($\pm 0.7^{\circ}\text{C}$); and early institution of an aerobic and resistive exercise program. Several pharmacotherapeutic options are also available to further reduce erosion of lean body mass (**W. B. Norbury et al, 2006**).

Since rehabilitation exercise training (RET) is considered the cornerstone of treating post burn patients, it has been proven that it has a great effect on restoring lean body mass, glucose, insulin resistance and protein metabolism. due to improvements in acute burn care over the last few decades, most patients with severe burns (up to 90% of the total body surface) survive. However, the metabolic

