and cardiovascular complications that accompany a severe burn can persist for up to three years post injury. Accordingly, there is now a greater appreciation of the need for strategies that can hasten recovery and reduce long-term morbidity post burn. RET (including resistance exercise and aerobic exercise) is a vital maneuver to restore normal body metabolism and glucose sensitivity in burn survivors. Given that RET is a safe and efficacious treatment that restores function and reduces post burn morbidity, the purpose is that a long-term exercise prescription plan should be considered for all patients with severe burns (**Alen Palackic et al, 2021**).

Chapter III

Subject, Materials and Methods

In this part of the study, the materials and methods will be presented under the following headings: subjects, equipment, procedures of the study and the statistical procedures.

Sample size

Sample size calculations will be performed using G*Power statistical software (version 3.1.9.2, Franz Faul, University Kiel, Germany) and will be revealed that the appropriate sample size for this study is N=68 patients, will be divided into two groups each consist of 34 patients, using the following assumptions: alpha level = 0.05, power = 0.90, effect size (Cohen's d) = 0.80, and two-tailed test.

Subjects

sixty-eight patients, who have upper limb, upper chest and upper back burn. Their ages will be ranged from 18-35 year old. Only patients around (20% - 40%) of total body surface area (TBSA) burned. The participants will be selected from government hospitals (General and insurance hospitals) and randomly distributed into 2 equal groups (group A, group B).

Design of the study:

In this study, the patients will be randomly assigned into two equal groups (34 patients for each group).

1.1_(a) Group A: (Study group)

This group includes 34 patients who have insulin resistance and who will receive resistance exercise and routine medical treatment. The patients will receive 3 sessions per week for 12 weeks, time of the session is 30 minutes.

1.1(b) Group B: (Control group)

This group includes 34 patients who have insulin resistance and who will receive routine medical treatment.

1.2 Criteria for Patients selection.

The criteria for patients selection are classified into two various criteria:

1.2 (a) Inclusion criteria

- Patients ranged from 18-35 years of age.
- Patients has waist hip ratio around 0.8 in female and 0.95 in male.

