during the training period. The exercises will be performed included leg press, leg extension and leg curl. After an instruction period on correct exercise technique the patient will perform a warm-up to become familiar with the movement. Next, the weight will be progressively increased to which the patient can successfully perform four repetitions with correct technique. If four repetitions will be performed with correct technique a one minutes rest will be given and the weight will be increased. This will be repeated until the patient can perform three repetitions, with the fourth repetition not volitionally possible with correct technique, and the test will be terminated. The amount of weight lifted from the successful lift will be recorded as the individuals three repetition maximum. From this information, the basic 3 sets of 8-12 repetitions RM's were established.

Resisted Exercise Training Program

Rehabilitative exercise training will be performed as previously described. All exercises will be performed using free weights, elastic bands and variable-resistance machines. Modifications to exercises will be made when appropriate depending on the patient injury characteristics. The load will be gradually increased from 50-60% of 3RM at the beginning of the program up to 80-85% of 3RM (repetitions maximum) at the end of the program. All exercise sessions will be preceded by a 5-minute warm-up at <50% VO₂peak. No strength training activities will be permitted outside the supervised training session; however, both groups will be encouraged to maintain normal daily activities (**Justin P. Hardee et al, 2014**).

4- Statistical procedures:

- In this study, the mean, the standard deviation and the standard error will be calculated for all the patients (2 groups of the study) after the detected time of the study.
- The mean and the standard deviation will be used as a primary source of connecting facts about each parameter to measure central tendency.
- Repeated measure ANOVA test will be used to compare variables within each group to detect the level of significance in each group.
- Unpaired t-test to compare the variable between groups to detect significance level between two groups (comparison).
- The statistical package for social science (SPSS) will be utilized for data analysis and the level of significance set at 0.05 levels.

Reference

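### Recruitment spans two types of government hospital, but no hospital factor is stated in the allocation and the fixed unpaired t-test cannot carry one: a modest, cheaply avoidable loss of precision

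*Protocol*

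**What the plan says.** Chapter III, *Subjects*, recruits from more than one source: patients are "selected from government hospitals (General and insurance hospitals) and randomly distributed into 2 equal groups". *Design of the study* repeats the random assignment of 34 patients to each group. Neither section mentions stratification or blocking, by hospital, hospital type or anything else, and the method of randomisation is not described. The number of hospitals and their expected contributions are not given.

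Section 4, *Statistical procedures*, names one between-group method: "Unpaired t-test to compare the variable between groups to detect significance level between two groups (comparison". The other test named, a repeated-measures ANOVA, is run within each group and has no hospital term either.

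*Sample size* sets "alpha level = 0.05", power 0.90 and a Cohen's d of "0.80, and two-tailed test", and arrives at 68 patients. It does not say whether the SD behind that d is the total SD or the SD within a hospital.

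**The concern.** When patients come from distinct sources, source is an obvious candidate for explaining some of the outcome variance. The planned analysis leaves any such variance in the error term. With a single 34/34 allocation and no restriction by source, one group may also receive noticeably more patients of one hospital type, and the stated test cannot adjust for that.

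The statistical analysis plan is not at hand, and silence in the protocol on allocation detail would not be a finding by itself. The difference here is that the protocol does fix the between-group test, and that test cannot include a hospital term. At stake is how efficiently 68 patients are used and how easily the result can be read if the groups happen to differ in hospital mix. The validity of the p-value is not at stake.

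**Working it through.** **Inputs from the protocol.** Alpha 0.05, "and two-tailed test", power 0.90, d = 0.80, 34 patients per group, unpaired t-test.

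**Inputs assumed, because the documents give none.** Two hospital types with 34 patients each, and a difference δ in mean HOMA-IR between types of 0.2 to 1.0 within-hospital SD. The top of this range exceeds the planned exercise effect itself and is an upper scenario.

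**1. The plan's own figure.** Two-sample noncentral t: noncentrality = d·√(n/2) = 0.80 × √17 = 3.298, with 66 df and critical value 1.997. Power is 0.9015 at 34 per group and 0.8926 at 33 per group. N = 68 is reproduced and is the smallest equal-group size that reaches 0.90.

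**2. Chance imbalance.** If 34 of the 68 patients are of one type and allocation is an unrestricted 34/34 split, the number of that type in group A is hypergeometric(68, 34, 34). The between-group difference in share has SD = (2/34) × √(34 × 0.25 × 34/67) = 0.122, or 12 percentage points. A gap of 8/34 (24 points) or more has probability 0.089.

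The typical (one SD) shift of the estimate is 0.122 × δ, that is 0.02, 0.06 and 0.12 SD for δ = 0.2, 0.5 and 1.0. The standard error of the group difference is √(2/34) = 0.243 SD. In the roughly 9% tail, a 24-point gap shifts the estimate by 0.235 × δ, that is 0.05, 0.12 and 0.24 SD, or 6%, 15% and 29% of 0.80.

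**3. Power.** With a 50:50 split, the variance between types is δ²/4 in within-hospital units, so total SD = √(1 + δ²/4).

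- If 0.80 is in within-hospital SD units, the plain t-test works with d = 0.80 / total SD (66 df).
- If 0.80 is in total SD units, the model adjusted for type works with d = 0.80 × total SD (65 df).

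| δ | Total SD | Variance share | Plain t-test, 0.80 on within-hospital SD: d, power | Adjusted, 0.80 on total SD: d, power |
|---|---|---|---|---|
| 0.2 | 1.005 | 1% | 0.796, 0.899 | 0.804, 0.904 |
| 0.3 | 1.011 | 2% | 0.791, 0.895 | 0.809, 0.908 |
| 0.5 | 1.031 | 6% | 0.776, 0.884 | 0.825, 0.918 |
| 1.0 | 1.118 | 20% | 0.716, 0.828 | 0.894, 0.953 |

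On the first reading, adjustment restores 0.901. On the second, the plain t-test keeps its planned 0.90 and adjustment is a gain. If the types do not differ, the adjusted model has power 0.9014 against 0.9015. The adjusted figures assume that the groups are balanced within each type, which is what stratified allocation provides.

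**4. Validity.** In a simulation with four hospitals (8,000 runs per setting) and unrestricted 34/34 allocation, the plain t-test had type I error 0.046 to 0.051 for hospital variance shares of 0 to 20%, and the mean error of the estimate was about zero. If allocation was stratified but the t-test ignored the strata, the test became conservative: type I error 0.042 at a share of 10% and 0.034 at 20%.

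**The case against.** The strongest reply is that nothing is invalid here. Hospital differences balance in expectation under individual randomisation, and the t-test's standard error already contains the variance between hospitals, so its p-value allows for chance imbalance. A reader might infer that hospital confounds the exercise comparison; the design does not support that, and the simulation agrees. This part of the objection stands in full.

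The size is also open to challenge. The documents give no hospital difference, no number of hospitals and no split between types. At δ = 0.2 to 0.3 the change in power is below one percentage point on either reading of d. The plainest reading of a two-group Cohen's d is the SD that the t-test faces, and then no power is lost against plan. A persistent hospital difference would also show partly in baseline HOMA-IR, so adjusting for baseline would capture some of the gain computed above. All of this stands, and it makes the point a modest one.

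Two further inferences are tempting and should not be made:

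- **Laboratories.** One might infer that hospitals use different laboratories or assays. No section says so. The two HOMA-IR formulas are unit versions of one definition, and the measurement section does set a common fast and a fasting survey. That "All patients will be evaluated in the same way" appears only as a basic assumption does not show that it fails.
- **Hospital care as a driver of the outcome.** Usual medical care is not defined for the trial, and the literature review names burn treatments as "important targets for available treatments including: early excision and grafting" and more. Much of that list is acute care, whereas the trial enrols patients two months after the burn. The eligibility criteria also narrow age, BMI, burn extent, HbA1c and concurrent medication.

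Finally, the absence of stratification is read from a text that does not describe the randomisation at all. If allocation is in fact stratified, the analysis half of the point remains, because a t-test that ignores the strata is then conservative.

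**Conclusion.** The point holds as a loss of precision and a risk of chance imbalance, not as bias or an inflated false-positive rate. Recruitment from two hospital types is stated, no hospital factor is stated in the allocation, and the fixed t-test cannot include one.

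Under the assumed 34/34 split by type and a difference of 0.2 to 1.0 within-hospital SD, the gain in power from a hospital-type term runs from negligible (0.3 percentage points or less) to about 5 points if d = 0.80 is on the total SD, or about 7 points if it is on the within-hospital SD. The lower part of that range is as compatible with the documents as the upper. The change is worth making because it costs almost nothing in a trial sized at the minimum for its stated power, and because stratification can only be set up before patients are allocated.

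**What to change.** In *Subjects* and *Design of the study*, state that allocation is 1:1 in concealed permuted blocks, stratified by hospital type. Stratify by individual hospital instead only if there are few hospitals and each contributes enough patients to fill its blocks.

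In section 4, replace the unpaired t-test with a linear model for HOMA-IR containing group, the same stratification factor, and baseline HOMA-IR (already measured) as covariate. SPSS fits this as an ANCOVA. Make the two changes together: stratifying and then ignoring the strata gives a conservative test. If allocation is already stratified, say so and change only the analysis.

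The cost is one allocation list per stratum and an extra factor and covariate in the model, with no additional patients, visits or blood. One or a few degrees of freedom are lost. The groups may end slightly unequal: at 33/35 power is 0.9013 against 0.9015 at 34/34. With many small hospitals, incomplete blocks would weaken the balance, which is why hospital type is the safer default stratum.

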they were the main areas of burns research in the period leading up to the 1980s. Wound treatment, healing and scar problems were also prominent areas in the published literature at that time. The direct outcome of this earlier work was that various strategies to prevent hypovolemic shock were developed and incorporated into clinical practice. These involved phased fluid/colloid replacement regimens (**P.I. Jewo et al, 2015**).

Following an initial sympathetic-mediated shock of a severe injury, the ebb phase is accompanied by a depression in the metabolic rate and reduced tissue perfusion. Thereafter, the systemic inflammatory response becomes uncontrolled and is further exacerbated by tissue and organ dysfunction, which drives the patient into a hyper metabolic state—a “flow” phase, which persists after wound healing and may last up to 36mo after initial injury (**Culnan et al, 2018**).

Hyper metabolism is a classic yet highly complex and multifactorial challenge to overcome in patients with severe burns. The chronic increase of circulating stress mediators, such as catecholamines and glucocorticoids, drives a multiorgan hyper catabolic response resulting in lipolysis, glycogenolysis, and proteolysis leading to an insulin-resistant and lipotoxic state, which only worsens the hyper metabolic response in a futile cycle (**Knuth et al, 2021**).

If hyper metabolism cannot be curbed, the patient may succumb to sepsis and/or multi organ failure. Targeting skeletal muscle is central to mitigating hyper metabolism, as proteins and amino acids serve as a major fuel source following a severe burn. Mechanistically, this results from a substantial increase in muscle protein breakdown that grossly exceeds the rate of muscle protein synthesis (**Hollenberg et al, 2004**).

The enormous energy demand, measured by resting energy expenditure, is a typical finding in burn patients, with the increase in metabolism (hypermetabolism) dependent on the size of burn. In patients with a TBSA of less than 10%, resting energy expenditure remains at physiological levels, but for TBSA in excess of 40%, this rate is twice as high during acute admission. Having reached the maximum value, the resting metabolic rate in severely burned patients gradually declines, amounting to 150%, 140%, 120% and 110% of baseline at the time of burn wound healing, 6, 9 and 12 months after thermal injury, respectively (**Wojciech Zwierello et al, 2023**).

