Burns affect nearly 300 million patients annually worldwide, with an associated substantial mortality. In the USA half a million Americans per year get burned, with approximately 40,000 requiring hospitalization. Thermal injuries induce systemic bimolecular changes with profound physiological alterations, such as increased muscle and bone catabolism, hepatic steatosis, higher susceptibility to infections, multiple organ dysfunction, insulin resistance and sepsis. The hyper metabolic response, a profound increase in metabolic demand reflected by an elevated resting energy expenditure (REE), is the primary contributor to aforementioned complications, and can persist for up to 3 years after a severe burn.

The metabolic changes following burns are not dissimilar to other traumas but very different in terms of their extent and persistence; characterized primarily by an ‘ebb’ phase within 48 h where metabolism, cardiac output and oxygen consumption are all decreased. This is typically followed by a ‘flow’ phase at around 120 h post-burn, where these variables gradually increase and plateau. For instance, the acute response allows vital organs to conserve energy, and mild to moderate hyperglycemia provides fuel for the brain and immune system after trauma. Burn

injuries, however, stand out in their intensity and duration. The chronic persistence of the hyper metabolic response, which appears to be driven by catecholamine, stress hormones, and pro-inflammatory cytokines, far surpasses the ability of the patient to respond, and physiological exhaustion ensues. Augmented rates of glycolysis, lipolysis and proteolysis induce a loss of lean and total body mass which subsequently causes immune dysfunction, decreased wound healing and severe infections. Left untreated, the amalgamation of these systemic injuries leads to organ dysfunction, sepsis and death (**Christopher Auger et al, 2017**).

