- Patient has body mass index (BMI around 25 kg/m²) (**J Obes Weight Loss Ther, 2015**).
- Patients has second degree thermal burn injury (superficial and deep partial thickness).
- Patients with around (20% - 40%) of total body surface area (TBSA) burned.
- Patients who are able to follow verbal commands.
- Patients will have upper limb, upper chest and upper back burn.
- Patients with normal hemoglobin A1C (5.6 %).
- Patients should take diet rich protein, omega 3 and should have good sleep.
- Patients passed two months post severe burns (**Melanie G. Cree et al, 2008**).

1.2 (b) Exclusion criteria

- Potential participants were excluded if they reported a leg amputation, anoxic brain injury, psychological disorders, quadriplegia, or severe behavior or cognitive disorders history of heart disease, stroke, diabetes mellitus, or any condition that would prevent them from engaging in an exercise study.
- Patients with liver disease, pancreatic disease or any disease affects metabolism.
- If they were already engaging in 2 or more planned exercise sessions per week.
- Patients with any medication to lower glucose levels. Blood pressure and medications to lower lipid levels (**Lance E. Davidson et al, 2009**).

2. Equipment and Tools:

Equipment in this study will be divided into two main categories; therapeutic and measuring equipment.

2.1. Therapeutic Equipment:

Resisted exercise program will be done by using:

- 1- Sand bags.

- 2-Elastic bands.

3- Resistance machines.

2.2. Measuring Equipment:

The following tools are used to assess the insulin resistance:

-HOMA-IR analysis will be used to assess insulin resistance by taking

Blood sample using sterile syringe 5 cm (**Pilar Gayoso-Diz et al, 2013**).

3. Procedures of the study:

The procedures of this study are classified into the following:

3.1 Measurement Procedures:

In this phase HOMA-IR analysis measurements:

All measurements will be taken before the treatment program, 6 weeks after the beginning of treatment program and 12 weeks after the beginning of the treatment program.

Assessment of insulin resistance:

- By doing HOMA-IR analysis.

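### Time since burn is used only as a two-month entry minimum; it enters neither the allocation nor the between-group test, although the protocol describes a post-burn metabolic response that declines over the first year

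*Protocol*

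**What the plan says.** **Eligibility (Chapter III, 1.2 (a) and (b)).** The timing criterion is "Patients passed two months post severe burns". No inclusion or exclusion criterion gives a maximum.

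**Allocation (Design of the study).** "the patients will be randomly assigned into two equal groups (34 patients for each group". No stratification factor is named. Both groups are described as having insulin resistance; of the control group the protocol says "This group includes 34 patients who have insulin resistance and who will receive routine medical treatment".

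**Assessments (3.1).** HOMA-IR is measured before treatment and "6 weeks after the beginning of treatment program and 12 weeks after the beginning of the treatment program".

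**Analysis (4, Statistical procedures).** A repeated-measures ANOVA is run within each group, and an unpaired t-test compares the groups. Neither is said to use a covariate.

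**Natural course.** The introduction says that resting metabolic rate in severely burned patients declines, "amounting to 150%, 140%, 120% and 110% of baseline at the time of burn wound healing, 6, 9 and 12 months after thermal injury". It describes a hypermetabolic phase "which persists after wound healing and may last up to 36mo after initial injury". The literature review says that this response "can persist for up to 3 years after a severe burn". The background sections also list insulin resistance among the metabolic changes that follow a burn.

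**The concern.** Patients who enter at ten weeks, seven months or several years after the burn can all qualify. On the protocol's own account they may be at different points of a response that is still resolving. Where the natural course differs between patients, their 12-week HOMA-IR will differ for reasons unrelated to exercise.

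Three things follow:

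- Variance linked to time since burn stays in the error term of the between-group t-test, although it could be removed.
- With 34 per group the arms can differ in timing by chance, and a reader of the result would then have reason to doubt it.
- A fall in HOMA-IR within the exercise group cannot be credited to exercise by the within-group ANOVA, because untreated patients would be expected to recover over the same 12 weeks.

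The protocol already treats timing as relevant, since it sets a minimum. It then makes no further use of it.

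**Working it through.** **1. The planned sample size.** Inputs from the Sample size section: d = 0.80, two-sided alpha 0.05, power 0.90, N = 68. For a two-sample t-test with n per group, df = 2n − 2 and the noncentrality is d·√(n/2). For n = 34 this is 0.80 × √17 = 3.30 on 66 df, and power is 0.9015. For n = 33 power is 0.8926. So 34 per group, 68 in all, is reproduced exactly.

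**2. What adjustment is worth.** Let R² be the share of variance in 12-week HOMA-IR that time since burn explains. The protocol gives no value, so R² = 0.1, 0.2 and 0.3 are assumptions.

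*(a) d = 0.80 refers to the enrolled, mixed population.* Adjustment shrinks the residual SD by √(1 − R²), so the effective d is 0.80/√(1 − R²).

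| R² | effective d | power at 34 per group |
|---|---|---|
| 0 | 0.800 | 0.902 |
| 0.1 | 0.843 | 0.929 |
| 0.2 | 0.894 | 0.953 |
| 0.3 | 0.956 | 0.973 |

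The one or two degrees of freedom spent on the covariate are ignored here; out of 66 they matter little.

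*(b) d = 0.80 was set for patients at a similar time since burn.* Mixing times adds variance, and an unadjusted test has d = 0.80 × √(1 − R²).

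| R² | d, unadjusted | power at 34 per group | n per group for 0.90 |
|---|---|---|---|
| 0.1 | 0.759 | 0.869 | 38 |
| 0.2 | 0.716 | 0.828 | 43 |
| 0.3 | 0.669 | 0.776 | 48 |

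The protocol does not say which SD its d rests on. Reading (a) is the natural one.

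**3. Chance imbalance.** The standardised difference in mean time since burn between two randomised groups of 34 has standard error √(2/34) = 0.243. It exceeds 0.25 SD with probability 0.30 and 0.5 SD with probability 0.04. If half of the 68 patients were early (an assumption), the hypergeometric probability of a 21 to 13 split or worse, in either direction, is 0.089; for 20 to 14 or worse it is 0.225.

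**4. How uneven the natural course could be.** The only month-by-month figures in the protocol are for resting metabolic rate. Take 150, 140, 120 and 110% at 2, 6, 9 and 12 months, and 100% at 36 months. Placing 150% at 2 months and 100% at 36 months is assumed. With 12 weeks = 12/4.345 = 2.76 months and straight lines between the points, the untreated 12-week fall is:

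- entry at 2 months: (10/4) × 2.76 = 6.9 points
- entry at 6 months: (20/3) × 2.76 = 18.4 points
- entry at 9 months: (10/3) × 2.76 = 9.2 points
- entry at 12 months or later: (10/24) × 2.76 = 1.15 points

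This shows that the protocol's own account implies a natural course that depends on entry time. It does not measure the effect on HOMA-IR.

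**The case against.** **The figures are for another quantity and probably another population.** They are resting metabolic rate, not HOMA-IR, and nothing in the protocol says that insulin resistance follows the same curve. They describe severely burned patients and come directly after a sentence on burns above 40% of body surface, whereas this trial enrols about 20–40%. A reader might infer from step 4 that the natural change in the endpoint varies more than tenfold between patients. The documents do not support that. This objection stands, which is why the size above rests on an assumed R².

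**Randomisation deals with imbalance.** In expectation it does, and the 5% error rate of the t-test already allows for chance imbalance. A reader might infer that the comparison is biased; it is not. The probabilities in step 3 describe how often the arms would look unequal, not how often the conclusion would be wrong. What remains is lost precision and a harder interpretation.

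**Fine strata would not track the proxy.** The fall in step 4 rises and then drops: entry at 10 months gives about 7.0 points, close to the 6.9 at 2 months. This stands, and it argues for few strata and for a covariate rather than a detailed scheme.

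**A wide window is a legitimate choice.** A reader might infer that patients beyond 36 months should be excluded. The text says only that the response "may last up to 36mo after initial injury", which sets no end date for insulin resistance. Entry also requires insulin resistance and excludes diabetes and diseases affecting metabolism, which screens out some late patients, although no HOMA-IR entry threshold is given. An upper limit trades generalisability for homogeneity.

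**Covariates may be left to the analysis plan.** Often they are, and an analysis plan may exist. But this protocol itself names an unpaired t-test as the between-group comparison, and allocation factors belong in a protocol.

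**Conclusion.** The point holds as a matter of efficiency and interpretation. Time since burn has a two-month minimum and no further role, although the protocol's background gives reason to expect that it is prognostic. There is no systematic bias between the groups.

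If d = 0.80 refers to the enrolled population, N = 68 stands, and using time since burn would raise power from 0.90 to about 0.93, 0.95 or 0.97 for an assumed R² of 10, 20 or 30%. A reader might infer from reading (b) in the working that the trial is too small. That requires d to have been set on a narrower population, which the protocol does not say.

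The gain could be smaller than shown if time since burn explains less than 10%, or if baseline HOMA-IR already carries much of the same information. The limit on the within-group ANOVA does not depend on R²: as long as some natural recovery occurs, it cannot isolate the effect of exercise.

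**What to change.** 1. Record time since burn at baseline as a variable. The burn date is already needed to apply the two-month rule.
2. Stratify the 1:1 allocation by it with few strata, for example two, and carry the factor into the analysis.
3. At minimum, whether or not allocation is stratified, replace the unadjusted between-group t-test with an ANCOVA of 12-week HOMA-IR that includes baseline HOMA-IR and time since burn.
4. State that the conclusion rests on this between-group comparison and that the within-group ANOVA is descriptive.

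The cost is one or two degrees of freedom and a slightly more complex allocation list. The sample size need not change. Whether to set an upper limit on time since burn is for the investigators and is not part of this fix.
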